### 1115 7.2 Primary Objective and Hypothesis

1116 The primary objective is to determine if participants with ET greater at near who are prescribed  
1117 SVLs and BFLs have different failure probabilities by 36 months.

1118 The primary outcome is treatment failure by 36 months, defined as meeting any one of the  
1119 following criteria at any follow-up visit from 3 months to 36 months inclusive:

- 1120 1. Constant ET  $\geq 15\Delta$  by SPCT at distance. (NOTE: intermittent ET and esophoria of any  
1121 magnitude are NOT considered failures.)
- 1122 2. Decrease in near stereoacuity on the Randot Preschool Stereoacuity (RPS) Test of 2 or  
1123 more levels from baseline, or from 960" at baseline to nil (see Table 2 in section 3.5 for  
1124 reference).
  - 1125 • At follow-up visits, the best of two stereoacuity measures in OFFICE spectacles  
1126 will be used.
  - 1127 • Baseline stereoacuity is defined as the near stereoacuity recorded with +3.00 D  
1128 power added to the participant's enrollment distance spectacle correction in trial  
1129 frames.
  - 1130 • Approximately 50% of participants are expected to have nil near stereoacuity at  
1131 baseline; it is acknowledged that these participants will not be able to meet the  
1132 near stereoacuity failure criteria.
- 1133 3. Binocular diplopia with a frequency of "more than 2 times per day" over the last week at  
1134 distance or near, by parental report.

1135 If nonsurgical or surgical treatment for ET other than the randomized treatment is before meeting  
1136 failure criteria, that participant will be considered a failure at the visit that such treatment is  
1137 prescribed.

1138 The study is designed as a superiority study to evaluate a 2-sided primary null hypothesis that the  
1139 failure probability by 36 months is the same between the SVL and BFL groups versus the  
1140 alternative hypothesis that it is different:

1142

1143  $H_{\text{null}}$  BFL% of failure by 36 months = SVL% of failure by 36 months

1144

$H_{\text{alternative}}$  BFL% of failure by 36 months  $\neq$  SVL% of failure by 36 months

1145

1146 The composition of the treatment failures (i.e., whether due to distance motor failure, near  
1147 stereoacuity failure, or diplopia "more than 2 times per day" over the last week) is also of  
1148 primary interest. However, the failure criteria may be interrelated and thus there is no specific  
1149 hypothesis for each criterion.

1150

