### 1151 7.3 Sample Size

1152 Sample size estimation is based on data from the retrospective cohort study conducted by  
1153 Whitman et al. After approximately 4 years of follow-up, 15.6% of the BFL group and 3.9% of

1154 the SVL group underwent strabismus surgery, all of whom had an increase in the distance angle  
 1155 of deviation to more than  $10\Delta$  by PACT (average increase from baseline was  $25\Delta$  in the BFL  
 1156 group and  $20.5\Delta$  in the SVL group). In the current study, the primary outcome is based on  
 1157 distance motor failure (based on SPCT), near stereoacuity failure, or diplopia “more than 2 times  
 1158 per day” over the last week by 36 months. Given a shorter follow-up, the proportion of distance  
 1159 motor failures may be less than that found in the Whitman et al. study. The proportion of near  
 1160 stereoacuity failures is believed to be less in the BFL group than the SVL group, but no data are  
 1161 available to provide estimates of the failure proportion for each group.  
 1162

1163 Table 4 shows the sample size estimates under various assumptions for the primary outcome in  
 1164 the SVL group and the difference in the primary outcome between the BFL and SVL groups. To  
 1165 be conservative, the total sample size needed to detect a treatment group difference is calculated  
 1166 using a two-sided Pearson chi-square test with a type I error rate of 5% and 90% power. Power is  
 1167 expected to increase slightly using a time-to-event approach for the primary outcome analysis.  
 1168

1169 **Table 4. Total sample size needed to detect a treatment group difference in proportions of  
 1170 failure by 36 months under various assumptions**

% of Failure in SVL Group	Treatment Group Difference in % of Failures (BFL – SVL)							
	5%	6%	7%	8%	9%	10%	15%	20%
3%	870	656	518	424	356	306	172	116
4%	1018	756	592	480	400	342	186	124
5%	1164	856	664	534	442	376	202	130
6%	1304	954	734	588	484	408	214	138
7%	1442	1140	802	640	524	440	228	146
8%	1576	1140	870	690	564	472	242	152
9%	1708	1230	936	740	602	502	254	158
10%	1836	1318	998	788	640	532	266	164
11%	1960	1402	1060	834	676	562	278	172
12%	2082	1486	1120	880	712	590	290	178
13%	2198	1566	1178	924	746	618	302	182
14%	2314	1644	1236	966	780	644	312	188
15%	2424	1720	1290	1008	812	670	322	194

1171  

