 1172 Assuming a failure probability of 5% in the SVL group and 15% in the BFL group, a sample size  
 1173 of 376 (188 per group) provides 90% power to detect a treatment group difference with a two-  
 1174 sided type I error rate of 5%. The total sample size is increased to 444 (222 per group) to account  
 1175 for up to a 15% loss to follow-up over 36 months.

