## 1194 **7.5 Analysis Dataset**

1195 The primary efficacy analysis will follow an intent-to-treat (ITT) principle. All randomized  
1196 participants will be included in the primary analysis dataset and analyzed according to the group  
1197 they were originally assigned, regardless of what treatment (if any) they received.

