## 1198 **7.6 Analysis of Primary Outcome – Treatment Failure by 36 Months**

1199 There may be participants who are lost to follow-up before their 36-month primary outcome data  
1200 are collected. To use the data collected from these participants before they are lost to follow-up,  
1201 a time-to-event analysis will be performed for the primary outcome. For participants who meet  
1202 failure criteria before or at the 36-month Primary Outcome Visit, time to treatment failure will be  
1203 defined as the time from randomization to the visit at which the failure is confirmed (either at the  
1204 initial visit or later at a Failure Confirmation Visit because the spectacle correction must be  
1205 updated [section 3.6]). If a participant is prescribed non-randomized treatment for ET before  
1206 meeting failure criteria, they will be considered a failure at the time when such treatment is  
1207 prescribed. Participants lost to follow-up are considered censored at the time of their last  
1208 recorded visit. If a participant is lost to follow-up before failure is confirmed, they will be  
1209 censored at their last visit for the primary analysis.

1210 The hazard ratio of treatment failure for treatment with BFLs versus SVLs and a two-sided 95%  
1211 confidence interval (CI) will be estimated with a Cox proportional hazards model. The model  
1212 will be adjusted for baseline near stereoacuity by the Randot Preschool Stereotest (RPS) in +3.00  
1213 D trial frames and baseline magnitude of the distance esodeviation by SPCT. The treatment  
1214 group difference in the probability of failure and a two-sided 95% CI will be estimated using the  
1215 direct adjustment method. The proportional hazards and functional form assumptions will be  
1216 evaluated.

1217 The timing and composition of failures (distance motor, near stereoacuity, diplopia, starting non-  
1218 protocol treatment) will be tabulated by treatment group to aid in the interpretation of the  
1219 treatment group difference for failure probability by 36 months.

1220 **7.6.1 Sensitivity Analyses for Primary Outcome**

1221 As a sensitivity analysis, if a participant meets the failure criteria prior to a required spectacle  
1222 update but is lost to follow-up before the failure is confirmed, the participant will be treated as a  
1223 failure at the time when they initially met the failure criteria (suspected failure). The primary  

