1224 analysis will be repeated with these unconfirmed failures being counted as failures.

1225 As an additional sensitivity analysis, treatment crossovers (BFL group participants who have  
1226 bifocals formally discontinued and begin to wear SVL; SVL group participants prescribed  
1227 bifocals) that occur before meeting any of the clinical measures for failure will be censored at the  
1228 visit date when treatment crossover occurred.

1229 **7.6.2 Contingency Plan for Primary Outcome**

1230 If the assumptions for the Cox model are not satisfied, an exact logistic regression model with  
1231 the same covariates will be attempted. If the adjusted model fails to converge, a model will be fit  
1232 without the adjustment for covariates. If the exact logistic regression still fails to converge,  
1233 Barnard's exact test will be performed.

1234 **7.7 Analysis of Secondary Outcomes**1235 **7.7.1 Binocular Function Test Score in BFLs at the Secondary Outcome Visit**

1236 A secondary outcome is the binocular function test score at the Secondary Outcome Visit (Post-  
1237 failure Secondary Outcome visit if failed or 38-month Secondary Outcome Visit if not failed).  
1238 The test score is assigned on an ordinal scale that combines the results of the RPS test, Random  
1239 Dot Stereo Butterfly test, and Preschool Worth 4-shape (W4S) test that were measured using the  
1240 bottom portion of the participants' BFLs. Given that BFLs can potentially reduce the magnitude  
1241 of near ET, which might in turn improve near stereoacuity, it was felt critical to measure  
1242 binocular function after a period of BFL wear in both treatment groups. Consequently, after 36  
1243 months of SVL or BFL wear, the SVL group will be prescribed BFLs, the BFL group will  
1244 continue wearing their BFLs, and both groups will be re-assessed at the 38-month Secondary  
1245 Outcome Visit. Because participants who meet failure criteria for the primary outcome at a prior  
1246 visit must be released to treatment at investigator discretion, these participants will be prescribed  
1247 BFLs (if in the SVL group) or continue in BFL (if in the BFL group) and return within 2 months  
1248 after meeting failure criteria for a Post-failure Secondary Outcome Visit.

1249 The possible levels of binocular function will be 48, 72, 120, 240, 480, 960 arcsec (RPS test),  
1250 2400 arcsec (Random Dot Stereo Butterfly test), and 10,000 or 100,000 arcsec (fusion or  

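### If the Cox assumptions fail, section 7.6.2 falls back on binary methods that cannot use censored follow-up and do not return the adjusted 36-month difference

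*Protocol*

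**What the plan says.** Protocol section 7.2 states the null hypothesis that "failure probability by 36 months is the same between the SVL and BFL groups versus the" alternative that it differs. Section 7.5 says that all randomized "participants will be included in the primary analysis dataset and analyzed according to the group" to which they were assigned.

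Section 7.6 gives its reason for a time-to-event analysis: "To use the data collected from these participants before they are lost to follow-up". Children lost to follow-up are censored at their last recorded visit, including those lost before a suspected failure is confirmed. A Cox model adjusted for baseline near stereoacuity and distance deviation gives the hazard ratio. The treatment "group difference in the probability of failure and a two-sided 95% CI will be estimated using the" direct adjustment method. Proportional hazards and functional form are both to be evaluated.

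Section 7.6.2 sets the fallback: "If the assumptions for the Cox model are not satisfied, an exact logistic regression model with" the same covariates. If that does not converge, the model is fitted "without the adjustment for covariates. If the exact logistic regression still fails to converge", Barnard's exact test follows. The section distinguishes neither type of assumption failure. It does not say how a child censored before 36 months is classified, and it names no replacement for the adjusted difference.

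**The concern.** The fallback gives up what section 7.6 set out to keep. Failures confirmed before loss still count in a binary analysis, but event-free time before loss does not. Unless status is imputed, which 7.6.2 does not mention, a lost child must be excluded, which conflicts with 7.5, or counted as a non-failure, which treats unseen follow-up as success.

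The effect measure changes too. Exact conditional logistic regression yields an odds ratio and conditions out the intercept, so direct adjustment does not carry over. Barnard's test is unadjusted and comes with no stated estimate.

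The remedy also does not match the trigger. Non-proportional hazards do not invalidate censoring. A wrong functional form is a covariate-coding problem, and carrying the same covariates into a logistic model does not cure it.

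At stake are the primary conclusion and, through the gatekeeping in 7.7.1, whether the binocular function score may be tested at all.

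**Working it through.** **Design figures (section 7.3).** SVL 5%, BFL 15%, two-sided 5%, 90% power. Per arm, n = [1.960·√(2·0.10·0.90) + 1.282·√(0.05·0.95 + 0.15·0.85)]² / 0.10² = (0.8315 + 0.5361)² / 0.01 = 187.05, so 188 per arm and 376 in total. Allowing "for up to a 15% loss to follow-up over 36 months": 188/0.85 = 221.2, so 222 per arm and 444 in total. Both figures reproduce.

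**What a binary status does to the proportions.** Let p be the true 36-month failure probability, d the loss spread uniformly over 36 months, and m the mean month of failure.

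- Lost counted as non-failures: observed failure proportion = p·(1 − d·m/36).
- Lost excluded: that quantity divided by itself plus (1 − p)(1 − d).

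*Equal 15% loss, similar timing (m = 18).* Non-failure coding: SVL 5% × 0.925 = 4.6%, BFL 15% × 0.925 = 13.9%, difference 9.2 to 9.3. Exclusion: 4.625/(4.625 + 80.75) = 5.4% and 13.875/(13.875 + 72.25) = 16.1%, difference 10.7.

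*SVL failures in months 0-12 (m = 6), BFL in months 18-36 (m = 27), equal 15% loss.* Non-failure coding: 5% × 0.975 = 4.9% and 15% × 0.8875 = 13.3%, difference 8.4. Exclusion: 4.875/85.625 = 5.7% and 13.3125/85.5625 = 15.6%, difference 9.9. Equal loss removes more of the later arm's failures.

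*Loss 5% SVL, 25% BFL, similar timing.* Non-failure coding: 4.9% and 13.1%, difference 8.2 to 8.3. Exclusion: 4.875/95.125 = 5.1% and 13.125/76.875 = 17.1%, difference 11.9.

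**Simulation.** 4,000-5,000 trials per scenario, 222 per arm, failures detected at the scheduled visits (3, 6, 9, 12, 18, 24, 30, 36 months), non-informative uniform dropout. Detection at the next visit makes the results slightly smaller than the hand figures.

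| Scenario (true difference 10 points) | Lost excluded | Lost as non-failures | Kaplan-Meier |
|---|---|---|---|
| Equal 15% loss, similar timing | 10.6 | 9.1 | 10.0 |
| Loss 5% SVL / 25% BFL | 11.6 | 8.0 | 9.9 |
| SVL early, BFL late, equal 15% loss | 9.7 | 8.3 | 10.0 |

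- *Children without status.* At equal 15% loss, about 64 of 444 (14%) end with no observed failure and no 36-month status. About 58 of them had at least one follow-up visit, and 42 were seen at 12 months or later.
- *Power, equal loss and similar timing.* Conditional exact 91-92%, Barnard 93%, Kaplan-Meier 93%.
- *Power, SVL early and BFL late.* In the order excluded, non-failures: Barnard 88%, 87%; conditional exact 86%, 84%. Kaplan-Meier 93%. With timing reversed, binary power is 95-97% and the difference is 11.6 or 10.2.
- *Type I error, equal loss.* 5-6%.
- *Type I error, 5%/25% loss.* Barnard 6.3-6.6% (true 10% in both arms) or 6.9-7.3% (true 15%); conditional exact 5.1-5.2% or 5.7-6.6%; Kaplan-Meier 4.9-5.2%.
- *Type I error, 5%/25% loss plus opposite timing, worse coding.* Barnard about 10%; conditional exact 8.2% (true 10%) to about 12% (true 15%); Kaplan-Meier about 5%.

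A second simulation (20,000 trials, constant hazard, exponential loss, chi-square as the binary test) gave the same picture. Equal 15% loss: 10.6, 9.1 and Kaplan-Meier 10.0, power about 93% for all. Loss 10% SVL / 20% BFL: 11.1, 8.6 and 10.0. True 15% in both arms with 5%/25% loss: type I error 6.5% (excluded), 8.2% (non-failures) and 4.9% (Kaplan-Meier).

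**Odds ratio against difference.** The design odds ratio is (0.15/0.85)/(0.05/0.95) = 3.35. It corresponds to 6.4, 10.0, 17.1 or 22.2 points at SVL risks of 3%, 5%, 10% or 15%, so an odds ratio alone does not supply the difference 7.6 promises.

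**The case against.** The strongest reply is that the protocol's own figures show little harm. The only loss given is up to 15% overall. With that loss equal across arms and similar timing, power and type I error barely move. The 5%/25% split and the complete separation of failure times are invented, and reversing the timing raises power. This stands: the larger effects are conditional, and the document does not show how often the fallback would be used.

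A binary comparison also fits the hypothesis, and the sample size was calculated "using a two-sided Pearson chi-square test with a type I error rate of 5% and 90% power. Power is" then said to rise slightly under a time-to-event analysis. Exact methods are a reasonable choice when events are few: 222 × 0.05 is about 11 SVL failures, and about 7 at the 3% that Table 4 allows. The largest inflation under unequal loss alone belongs to Barnard's test, the last step; the conditional exact test does better. The covariate-adjusted exact logistic model was not simulated. These points temper the size but do not restore the lost follow-up or the adjusted difference.

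Finally, coding of missing status and the accompanying estimate could be left to an SAP, and the conflict with 7.5 disappears if lost children are kept as non-failures or imputed. That is fair for those details. But the sequence of methods is fixed in the protocol, and the mismatch between trigger and remedy lies in that text.

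**Conclusion.** The concern holds. For any Cox assumption failure, section 7.6.2 prescribes methods that cannot use the partial follow-up 7.6 was designed to use, and it does not carry over the adjusted 36-month difference. Neither kind of assumption failure makes this necessary.

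In the base case the effect is under 1 point on a 10-point difference, with power above 90% and test size kept. It becomes material when failure timing differs by arm, a pattern that would itself trigger the fallback, or when loss differs by arm. Power then drops to 84-88% under early SVL and late BFL failure, and type I error reaches about 10% when both patterns combine.

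Some protocol features make these conditions possible. About half the children are expected to have nil baseline stereoacuity and cannot fail on that criterion. Stereoacuity failures are expected to favour BFL, while the surgery data cited in 7.3 ran higher with BFL. Families and treating investigators are unmasked. The likelihood remains unknown. All calculations assume non-informative loss; under informative loss Kaplan-Meier would be biased as well.

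**What to change.** Replace the paragraph in 7.6.2 with wording such as:

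> If proportional hazards is not satisfied, the groups will be compared by the difference in 36-month failure probability from direct adjustment of a Cox model stratified by treatment group with the same covariates, with a bootstrap or robust 95% CI. If this cannot be fitted, the Kaplan-Meier difference at 36 months, stratified by baseline near stereoacuity stratum, will be used. If functional form is not satisfied, the covariate will be re-specified within the Cox model, for example with nil stereoacuity as its own category.

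Keep exact logistic regression and Barnard's test only as a last resort or sensitivity analysis, and state there how children lost before 36 months are coded.

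The cost is one paragraph and no new data. The downside is reliance on large-sample or bootstrap inference with about 11 expected SVL failures, so exactness is given up. With true 5% in both arms and 15% loss, simulated type I error was 5.5% for Kaplan-Meier and 5.7% for Kaplan-Meier in two strata, with 94% CI coverage. The treatment-stratified Cox version was not simulated and should be checked before it is adopted.

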- 362 • Cylinder axis must be within  $\pm 10$  degrees if cylinder power is  $\leq 1.00$  D and within  $\pm 5$   
363 degrees if cylinder power is  $> 1.00$  D

364 **2.7 Randomization**

365 Eligible participants will be randomized 1:1 to the following:

- 366 1. Single vision spectacles (SVLs)
- 367 2. Bifocal spectacles (BFLs): +3.00 D flat-top bifocal add

368 The Jaeb Center will construct a separate Master Randomization List using a permuted block  
369 design stratified by presence/absence of stereoacuity of at least 960 arcsec or better on the  
370 Randot Preschool Stereoacuity Test conducted at near (33 cm) in a trial frame with +3.00 D  
371 added lenses.

372 A child is officially enrolled in the randomized trial when the website randomization process is  
373 completed.

374 **2.8 Prescription of Randomized Treatment**

375 Spectacles prescribed at enrollment will be referred to as the **HOME spectacles** for both  
376 treatment groups. These are the spectacles that the participants will have at home and be  
377 instructed to wear every day for all waking hours (at home, school, outside, etc.).

379 **Single-vision lens (SVL) group:**

380 Participants randomized to treatment with SVLs will be prescribed HOME spectacles meeting  
381 the following criteria based on their cycloplegic refraction:

- 382 • Full correction of hyperopia/myopia
- 383 • Full correction of astigmatism
- 384 • Full correction of anisometropia

385 Children in the SVL group with no refractive error (emmetropia or plano refraction) will be  
386 prescribed spectacles with plano lenses.

388 **Bifocal lens (BFL) group:**

389 Participants randomized to treatment with BFLs will be prescribed HOME spectacles meeting  
390 the following criteria based on their cycloplegic refraction:

- 391 • Full correction of hyperopia/myopia
- 392 • Full correction of astigmatism
- 393 • Full correction of anisometropia

- 394     • +3.00 D bifocal add (flat top, 35 mm with segment height set at mid-pupil - see *ETS3*  
395       *Manual of Procedures*)  
396        ○ Progressive addition lenses (PALs) are NOT allowed to be worn during the study.  
397

398 Children in the BFL group with no refractive error (emmetropia or plano refraction) will be  
399 prescribed spectacles with plano lenses and the +3.00 D bifocal add.

400 **Both treatment groups:**

401 The refractive error correction prescribed at the time of randomization must follow the  

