1251 suppression, respectively, indicated by Preschool W4S test). The binocular function test score  
1252 will be calculated by converting binocular function to a log value ranging from 1.68 (log of 48  
1253 arcsec) to 5.0 (log of 100,000 arcsec). Baseline near stereoacuity on the RPS test that was  
1254 measured through +3.00 D lenses will be used in the calculation of the binocular function test  
1255 score at baseline, and the Random Dot Stereo Butterfly and Preschool W4S tests that were also  
1256 measured through +3.00 lenses. The score at the Secondary Outcome Visit (Post-failure  
1257 Secondary Outcome visit if failed or 38-month Secondary Outcome Visit if not failed) and the  
1258 change from baseline will be tabulated for each treatment group. A treatment group comparison  
1259 of the scores will be performed using the exact Wilcoxon rank sum test to determine whether the  
1260 treatment groups have different distributions of the score. If the hypothesis test for the primary  
1261 outcome is significant, an alpha of 0.05 will be passed down to this test. If not, this outcome will  
1262 be exploratory with no *P*-value reported.

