### 1308 **7.8.1 Ocular Alignment at Distance and Near**

#### 1309 **7.8.1.1 Comparison of Randomized Treatments at 36 Months or Confirmed Failure**

1310 At the time of the primary outcome (36 months or confirmed failure), the magnitude of deviation  
 1311 by PACT and the change from baseline will be tabulated and described with summary statistics  
 1312 for each treatment group. The treatment group difference in the magnitude of deviation and the  
 1313 95% CI will be estimated using an analysis of covariance (ANCOVA) adjusting for the baseline  
 1314 PACT magnitude.

1315 The magnitude of deviation by SPCT and the change from baseline will also be tabulated and  
 1316 described with summary statistics for each treatment group. The proportions with constant ET of  
 1317  $\geq 10\Delta$ , constant ET of  $< 10\Delta$ , intermittent ET, esophoria, and orthophoria will be tabulated by  
 1318 treatment group.

1319 The above analyses will be performed separately for distance and near deviations as measured  
1320 through distance correction, to assess the magnitude of the underlying angle of deviation. In  
1321 addition, the near deviations as measured through OFFICE spectacles (i.e., SVLs with  
1322 cycloplegic refraction and +3.00 D power) will be analyzed similarly, to assess the impact of  
1323 +3.00 D lenses on the near deviation.

1324 **7.8.2 Binocular Function Test Score**

1325 **7.8.2.1 Subgroup Analysis of Secondary Outcome Binocular Function Score**

1326 The secondary outcome of binocular function test score in BFLs at the Secondary Outcome Visit  
1327 (Post-failure Secondary Outcome visit if failed or 38-month Secondary Outcome Visit if not  
1328 failed) as defined in section 7.7.1 will be further evaluated in subgroups specified in section  
1329 7.7.2.

1330 **7.8.2.2 Comparison of Overall Treatment Strategies at 38 Months**

1331 To evaluate real-world effectiveness of the overall treatment strategies the binocular function test  
1332 score at the 38-month Secondary Outcome Visit and the change from baseline will be tabulated  
1333 by treatment group. Distinct from the secondary outcome binocular function score (sections 7.7  
1334 and 7.8.2.1), this analysis will utilize the 38-month data for all participants, regardless of whether  
1335 they met failure criteria at a prior visit. Scores will be calculated using the same algorithm as  

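### The only alpha-bearing secondary test ignores the randomization stratum and the baseline score; it is valid, but a stratified rank test would be more powerful at no cost in data

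*Protocol*

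**What the plan says.** Section 7.7.1 builds a nine-level ordinal score: six Randot Preschool levels (48 to 960 arcsec), one Butterfly level (2400), and two Worth 4-Shape levels (10,000 for fusion, 100,000 for suppression). The same score exists at baseline, where near stereoacuity "measured through +3.00 D lenses will be used in the calculation of the binocular function test" score, together with the Butterfly and Worth 4-Shape results through the same add.

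The baseline score is used only descriptively: "change from baseline will be tabulated for each treatment group. A treatment group comparison", and the sentence continues "of the scores will be performed using the exact Wilcoxon rank sum test to determine whether the" groups differ in distribution. No stratum or covariate is named. This test receives alpha of 0.05 if the primary test is significant; otherwise no P-value is reported.

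Section 2.7 describes a permuted block "design stratified by presence/absence of stereoacuity of at least 960 arcsec or better on the" Randot Preschool test through +3.00 D. Section 7.2 adds: "Approximately 50% of participants are expected to have nil near stereoacuity at" baseline.

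Elsewhere baseline is used. The primary Cox model in 7.6 "will be adjusted for baseline near stereoacuity by the Randot Preschool Stereotest (RPS) in +3.00" D trial frames, and for the exploratory alternate cover test magnitude in 7.8.1.1 the group difference and "95% CI will be estimated using an analysis of covariance (ANCOVA) adjusting for the baseline" value.

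**The concern.** A child measurable on the Randot Preschool test through +3.00 D starts at 960 arcsec or better on this score, and a nil child starts at 2400 or worse. The two strata therefore occupy separate ranges of the baseline score. If the baseline level predicts the later level at all, the stratum is prognostic for this outcome.

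Stratified allocation then removes nearly all between-stratum difference between the arms, but the unstratified Wilcoxon test computes its null variance as if that difference could still occur. The test statistic varies less than its reference distribution assumes, so the test runs below 5% and gives up power that data already collected would recover. The protocol does use baseline for its primary outcome and for an exploratory one; the one secondary test that carries alpha does not, and no reason is given.

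**Working it through.** **The protocol's own figures.** Section 7.3 assumes failure of 5% (SVL) and 15% (BFL), two-sided 5%, 90% power:

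n per arm = [1.960·√(2·0.10·0.90) + 1.282·√(0.05·0.95 + 0.15·0.85)]² / 0.10² = (0.832 + 0.536)² / 0.01 ≈ 187, rounded up to 188, or 376 in total.

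Allowing "for up to a 15% loss to follow-up over 36 months": 376 / 0.85 = 442.4, rounded to 443 and to 444 as an even total. These figures reproduce. The protocol gives no power for the secondary score.

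**Closed form for the size of the planned test.** Let R² be the share of outcome rank variance explained by the stratum. With allocation balanced within strata, the true variance of the rank sum is about (1 − R²) times the nominal one, so

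size ≈ 2·[1 − Φ(1.96 / √(1 − R²))].

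For a median split of a normal baseline with baseline-outcome correlation ρ, R² ≈ (2/π)ρ² = 0.637ρ²:

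- ρ = 0.3: R² = 0.057, 1.96/0.971 = 2.02, size about 4.4%
- ρ = 0.5: R² = 0.159, 1.96/0.917 = 2.14, size about 3.3%
- ρ = 0.7: R² = 0.312, 1.96/0.829 = 2.36, size about 1.8%

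**Simulation.** From the protocol: 444 randomized 1:1 in permuted blocks within the stratum, 50% nil, 15% loss (about 377 evaluable), nine ordered levels. Assumed, because the protocol does not give them: blocks of 4, random loss, bivariate normal latent scores, the level cuts (two sets), ρ, and a 0.3 SD treatment shift. There were 10,000 trials per null setting (standard error about 0.2 points) and 4,000 per power setting (about 0.6 points). The van Elteren test sums the within-stratum rank statistics with weights 1/(stratum size + 1). Entries are percentages or percentage points; ranges are over the two sets of cuts.

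| Assumed ρ | 0 | 0.3 | 0.5 | 0.7 | 0.85 |
|---|---|---|---|---|---|
| Size, planned test | 4.8-4.9 | 4.4-4.6 | 3.6 | 2.2-2.3 | 1.0-1.1 |
| Power, planned test | 78-80 | 78-79 | 78-81 | 80-83 | 83-86 |
| Power, van Elteren | 78-80 | 79-81 | 83-85 | 89-91 | 96-97 |
| Power, rank ANCOVA (baseline score + stratum) | 78-80 | 80-82 | 86-87 | 94-96 | 99+ |
| Gain, van Elteren | 0 | 1-2 | 4-5 | 8-9 | 11-13 |
| Gain, rank ANCOVA | 0 | 3 | 7-8 | 13-14 | 13-17 |

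The size of the van Elteren test was 4.8-5.2% throughout.

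**Other settings.**

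- 376 participants, no loss, other cuts, shift 0.29 SD, ρ = 0/0.3/0.5/0.7: planned size 5.3/4.4/3.5/1.5%; power 75/77/79/81% planned, 76/78/83/90% van Elteren, 76/79/86/95% rank ANCOVA. With 30% nil and ρ = 0.5: planned size 3.7%; power 78, 83 and 86%.
- 444 randomized, 15% loss, a further set of cuts, ρ = 0/0.3/0.5/0.7/0.85: planned size 5.0/4.1/3.5/2.3/1.2%; gains 0/2/4/9/11 points (van Elteren) and 0/3/7/15/15 points (rank ANCOVA).
- Unequal effects (first cuts, ρ = 0/0.3/0.5/0.7/0.85), van Elteren minus planned: whole effect (0.6 SD) in the measurable stratum, 0/−1/+1/+3/+4 points; whole effect in the nil stratum, 0/+4/+10/+18/+28 points.
- Permutation versions in place of the normal approximation (2,000 trials, 999 permutations, ρ = 0.5 and 0.7): planned test size 3.5% and 2.4%, power 80% and 82%; van Elteren permuted within strata, size 4.3% and 5.0%, power 86% and 91%.

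**The case against.** The planned test is prespecified, needs few assumptions and is valid, so nothing in 7.7.1 is an error. That stands, and this point claims no more than lost efficiency.

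The comparison with other sections is imperfect: the alternate cover test result is a magnitude that suits ANCOVA, the Cox model concerns another outcome, and section 7.8 itself notes that binocularity outcomes may suit non-parametric methods. That is an argument against a linear model, not against a stratified rank test. The plain Wilcoxon test does address the marginal distributions directly, and proportional odds adds an assumption; this is a reason to keep the plain test as a sensitivity analysis.

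The stratum is not wholly ignored. Allocation is balanced on it, and section 7.8.2.1 examines the score in the 7.7.2 subgroups, which include nil versus measurable near stereoacuity. That analysis is exploratory and recovers no power for the alpha-bearing test.

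The size of the gain is uncertain. The protocol gives no correlation, effect or level distribution, and nothing in it supports 0.85 in particular. The gain also depends on the effect: at ρ = 0.5 a separate check (376 participants, 3,000 trials) gave about 7 points at 0.2 SD, 4-5 at 0.3 SD and 1 or less at 0.4-0.5 SD; at ρ = 0.3 it was 2 points or less throughout. The power figures are for the test on its own, whereas its P-value is reported only if the primary test succeeds, so the effect on a reported conclusion is somewhat smaller.

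Finally, section 9.2 requires IRB approval of any amendment, so the change is not entirely without effort.

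**Conclusion.** The point holds as an optional efficiency improvement. The planned test never exceeded 5% beyond simulation error, and its conclusion would not be biased. If the stratum is prognostic, which is likely because it is a cut of the score's own baseline, the test is conservative. Over correlations of 0.3 to 0.7 and a shift near 0.3 SD, it gives up about 1 to 9 power points against a stratified test and about 3 to 15 against a baseline-adjusted one. Those sizes rest on the assumed correlation, effect and level cuts; the direction was the same under every set of cuts tried. The worst case found for stratifying was a loss of about 1 point, close to simulation error. The statistical analysis plan was not available. If it already names a stratified or adjusted test, the protocol sentence needs to be reconciled with it.

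**What to change.** In 7.7.1, make the alpha-bearing test the van Elteren (stratified Wilcoxon) test by the randomization stratum, with permutation within strata if an exact P-value is wanted. If more efficiency is wanted, name instead a rank ANCOVA or proportional-odds model with stratum and baseline binocular function score. Choose one before any unmasked comparison, leave alpha at 0.05 and the gatekeeping as written, and report the plain exact Wilcoxon test as a sensitivity analysis.

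The cost is one sentence in the protocol and its IRB review. The stratum and baseline score are already collected, and sample size, visits and alpha do not change.
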